6.2.9 Clinician Global Impression of Improvement/Severity

The CGI-I/S is a global index that can be used to rate the severity of a specific condition (a single-state scale) from the clinician's perspective.

The CGIS for this study is a single question asking the clinician to rate the current state of the subject's overall asthma severity on a 7point scale (normal, borderline, mild, moderate, marked, severe, extreme). The CGII for this study is a single question asking the clinician to rate the subject's overall asthma status since the start of the study (ie, since baseline [Visit 2]) on a 7point scale (very much improved, much improved, minimally improved, no change, minimally worse, much worse, very much worse).

6.3 Safety Measures

Safety and tolerability assessments will include the frequency and severity of AEs as well as the evaluation of changes in clinical laboratory values and vital signs.

Time points for all assessments are summarized in [Table 2](#).

6.4 Pharmacodynamic and Biomarker, and Pharmacokinetic Assessments

Time points for all assessments are summarized in [Table 2](#).

6.4.1 Pharmacodynamics and Biomarkers

Serum samples will be analyzed for soluble LIGHT levels.

For a selected subset of sites or subjects, sputum samples will be analyzed for soluble LIGHT levels. Sputum samples may be evaluated for gene expression in the future. Biomarkers associated with inflammation will be collected and may be evaluated in the future, and samples for immunophenotyping of immune cell subsets in circulation will be collected and may be analyzed in the future.

6.4.2 Pharmacokinetics

Blood samples will be collected for measurement of AVTX-002 in plasma. Time points for collection are indicated in [Table 2](#).

6.5 Immunogenicity Measures

Immunogenicity will be evaluated by means of the incidence of measured ADAs. Time points for all assessments are summarized in [Table 2](#).

7 STUDY POPULATIONS

7.1 Analysis Populations

7.1.1 Randomized Analysis Set

The RAS will include all subjects who are randomized in the study. Subjects will be categorized according to their randomized treatment group. The RAS will be used for all disposition, protocol deviations, and demographic and other baseline characteristics analyses.

7.1.2 Safety Analysis Set

The SAS will include all subjects who are randomized in the study and receive at least one dose of investigational product. Subjects will be categorized according to their actual treatment group. The SAS will be used for all exposure, safety, and immunogenicity analyses.

7.1.3 Full Analysis Set

The FAS will include all subjects who receive at least one dose of investigational product and have a baseline and at least one post-baseline value of any of the efficacy assessments. Subjects will be categorized according to their randomized treatment group. The FAS will be used for all efficacy and PD analyses.

7.1.4 Per Protocol Analysis Set

The Per Protocol analysis set will include all subjects in the FAS who do not have significant protocol violations as determined by the sponsor as exclusionary from this analysis set prior to database lock (including, but not limited to, lack of compliance with study drug).

7.1.5 Pharmacokinetic Analysis Set

The PK Analysis Set will include all subjects who receive at least one dose of investigational product and have at least one postdose measurable plasma AVTX002 concentration. Subjects will be categorized according to their actual treatment group. The PK Analysis Set will be used for all PK analyses.

7.2 Subgroups

Occurrence of asthma related events will be evaluated in subjects with < 150 eosinophils/ μ L at baseline.

Sputum soluble LIGHT levels will be assessed in a select subset of subjects. Inclusion of subjects in this subset will be presented (as recorded in the eCRF as a subject consented to sputum sample collection and with at least one sputum sample being collected), although any results from sputum samples do not form part of the statistical analysis described in this SAP (see [Section 10.9](#)).

8 CHANGES IN CONDUCT OR PLANNED ANALYSES FROM THE PROTOCOL

The following changes from protocol conventions are applied:

1.

According to the Schedule of Assessments (Table 1 in study protocol), numbering of assessment day starts at Day 0 at Visit 2, Baseline; ie:

Procedure	Screening	...	Baseline		Doubleblind Treatment Period					
Visit	V 1	...	V 2	V 3	V 4	V 5	V 6	V 7	V 8	V 9/ET
Assessment Week	-4	...	0	1	2	4	6	8	12	14
Assessment Day	Appr -37	...	0	7	14	28	42	No later than 56	84	98

Appr = approximately; ET = early termination; V = Visit

For the purpose of presentation of the study results however, the first day of dosing will be denoted Day 1 (ie, there will be no Day 0). This results in the following changes to numbering of assessment day, according to which the study results will be reported:

Procedure	Screening	...	Baseline		Doubleblind Treatment Period					
Visit	V 1	...	V 2	V 3	V 4	V 5	V 6	V 7	V 8	V 9/ET
Assessment Week	-4	...	0	1	2	4	6	8	12	14
Assessment Day	Appr -37	...	1	8	15	29	43	No later than 57	85	99

Appr = approximately; ET = early termination; V = Visit

2.

According to protocol Section 11.1.1, an AE will be considered treatmentemergent if it occurs after the first dose of investigational product and within 28 days after a subject's last dose of investigational product. However, since the start time for AEs are collected in this study only if AE duration is < 24 hours, the definition for an AE to be considered treatmentemergent will be as follows:

- If AE start time is recorded: an AE will be considered treatmentemergent if it occurs on or after the time of first dose of investigational product and within 28 days after a subject's last dose of investigational product.
- If AE start time is not recorded: an AE will be considered treatmentemergent if it occurs on or after the date of first dose of investigational product and within 28 days after a subject's last dose of investigational product.

9 OVERALL STATISTICAL CONSIDERATIONS

9.1 General Conventions

Efficacy, safety, PK, PD, and immunogenicity variables will be summarized using descriptive statistics. Descriptive statistics for continuous data will include number of subjects (n), mean, SD, median, minimum, and maximum. Summaries of change from baseline variables will include only subjects who have both a baseline value and corresponding value at the time point of interest. Descriptive statistics for categorical data will include frequency and percentage. Data will be summarized by treatment group (AVTX-002 and placebo) and overall (where applicable).

Descriptive statistics for continuous data will be displayed with applicable decimal precision as follows in relation to the source data (N: number of decimals for source parameter value, with $0 \leq N \leq 3$):

- Number (n)
- Mean, Median: N + 1
- SD: N + 2
- Minimum, Maximum: N + 0

Statistical hypothesis testing is planned to be performed on only the primary endpoint (see [Section 10.6.1](#)).

Listings will be provided for all collected study data.

Although the protocol defines the first day of administration of study drug as Day 0 (Visit 2, Baseline), for datasets and the study results reporting, the first day of administration of study drug is defined as Day 1. All other study days will be computed relative to Day 1. The study day for a particular event or visit will be calculated as $Date_{event} - Date_{first\ dose} + 1$ (for event occurring on or after first dose), and $Date_{event} - Date_{first\ dose}$ (for events occurring prior to first dose). For concomitant medications, AEs, clinical laboratory and vital signs assessments, as well as efficacy, PK, and PD assessments which occurred or were performed on or after the date of last administration of study drug, the study day relative to last study drug dose will also be displayed, ie, $Day_{last} = Date_{event} - Date_{last\ dose}$. In case of missing or partial dates being recorded for an event, the study day will not be calculated and will appear as missing in the subject listings.

9.2 Baseline and Related Changes Definition

In general and unless otherwise specified, baseline is defined as the last available assessment prior to the first dose of the study drug.

CFB is calculated as: $CFB = observed\ value - baseline\ value$

CFB% is calculated as: $CFB\% = \left(CFB / \text{baseline value} \right) \times 100$ (if the baseline value is 0, CFB% cannot be calculated)

Where unscheduled/repeat assessments are relevant and exist for any subject at a particular visit they will also be considered in the baseline definitions, provided they remain prior to the first dose of study drug.

Visit 1a (Day 7 [2 days]) with diary activation was added to the protocol Schedule of Assessments in Protocol Version 4.0 (Amendment 3), 05 May 2022. Therefore, subjects enrolled prior to this amendment did not have a diary activated until the day of randomization (ie, they will not have diary entries during the 7 days preceding Visit 2). A baseline value cannot be calculated for subjects with no diary entries before the day of randomization. To include such subjects in analyses, additional definitions of baseline have been included in which Day 1 entries or Day 1 through Day 7 entries may be used for calculation of baseline when a subject does not have sufficient diary entries prior to Day 1. This approach has been taken given that all subjects have received a 30day regimen of stable asthma medications leading up to Day 1 which will be maintained until Day 14 per protocol; therefore, a Day 1 (or Day 1 through Day 7) diary entry is a reasonable representation of their baseline. The baseline definitions are detailed below for each of the following subject diary assessments:

Asthma Symptom Diary Assessment	Baseline Definition
Mean symptom score	Subjects with at least 1 morning diary entry and at least 1 evening diary entry from Day -7 through Day -1 for the applicable symptom, will have their baseline value calculated as: $\frac{\text{sum of available entries from Day -7 through Day -1}}{\text{number of available entries from Day -7 through Day -1}}$ When the above criteria are not met, subjects with at least 1 morning diary entry and at least 1 evening diary entry from Day -7 through Day 1 for the applicable symptom, will have their baseline value calculated as: $\frac{\text{sum of available entries from Day -7 through Day 1}}{\text{number of available entries from Day -7 through Day 1}}$ Otherwise, subjects who do not have at least 1 morning diary entry and at least 1 evening diary entry from Day -7 through Day 1 for the applicable symptom will have a missing baseline value.
Mean ASD score	Subjects with at least 1 morning diary entry and at least 1 evening diary entry from Day -7 through Day -1 for each of the 6 symptoms, will have their baseline value calculated as: $\frac{\text{sum of available entries from Day -7 through Day -1}}{\text{number of available entries from Day -7 through Day -1}}$ When the above criteria are not met, subjects with at least 1 morning diary entry and at least 1 evening diary entry from Day -7 through Day 1 for each of the 6 symptoms, will have their baseline value calculated as: $\frac{\text{sum of available entries from Day -7 through Day 1}}{\text{number of available entries from Day -7 through Day 1}}$

	Otherwise, subjects who do not have at least 1 morning diary entry and at least 1 evening diary entry from Day -7 through Day 1 for each of the 6 symptoms will have a missing baseline value.
Mean daily number of SABA puffs/inhalations	Baseline values will be calculated by the following 4 separate definitions. The primary baseline definition (Definition 1) will be used for all output that requires a comparison of SABA use to baseline. Definition 2 through 4 will only be used for the primary endpoint summary in the FAS and associated listings (ie, occurrence of an asthma related event; see Section 6.2.1).
	Definition 1 (primary baseline definition):
	
 Subjects whose diary was activated no later than Day -1, will have their baseline value calculated as: $\frac{\text{sum of daily sums from Day -7 through Day -1}}{\text{number of days the diary was available from Day -7 through Day -1}}$ Subjects for whom their diary was not activated by Day -1 but for whom the diary was activated on Day 1 and ≥ 1 Day 1 entry is available, will have their baseline value calculated as: $\frac{\text{sum of entries on Day 1}}{\text{number of days the diary was available from Day 1 through Day 1}}$ Subjects for whom their diary was not activated by Day 1, will have a null baseline.
	Definition 2:
	
 Subjects whose diary was activated no later than Day -1, will have their baseline value calculated as defined in Definition 1 above. Subjects for whom their diary was not activated by Day -1 but for whom the diary was activated for ≥ 1 day between Day 1 and Day 7, will have their baseline value calculated as: $\frac{\text{sum of daily sums from Day 1 through Day 7}}{\text{number of days the diary was available from Day 1 through Day 7}}$ Subjects for whom their diary was not activated by Day 7, will have a null baseline.
	Definition 3:
	
 Subjects whose diary was activated no later than Day -1, will have their baseline value calculated as defined in Definition 1 above. Subjects for whom their diary was not activated by Day -1, will have a null baseline.
	Definition 4:
	
 Subjects whose diary was activated no later than Day -4, will have their baseline value calculated as defined in Definition 1 above. Subjects for whom their diary was not activated by Day -4, will have a null baseline.
	Note: for the days the diary was available (ie, any day from diary activation through deactivation), all missing entries will be considered 0 for calculation of the baseline value
Mean peak flow rate	Baseline values will be calculated by the following 4 separate definitions. The primary baseline definition (Definition 1) will be used for all output that requires a comparison of peak flow rate to baseline. Definition 2 through 4 will only be used for the primary endpoint summary in the FAS and associated listings (ie, occurrence of an asthma related event; see Section 6.2.1).

Definition 1 (primary baseline definition):

- Subjects with ≥ 1 of the expected 7 entries from Day -7 through Day -1, will have their baseline value calculated as:

$$\frac{\text{sum of available entries from Day -7 through Day -1}}{\text{number of available entries from Day -7 through Day -1}}$$

- Subjects with no entries from Day -7 through Day -1 but for whom the Day 1 entry is available, will have their baseline value calculated as:

$$\text{Day 1 entry}$$

- For subjects with no entries from Day -7 through Day 1, the baseline value will be missing.

Definition 2:

- Subjects with ≥ 1 of the expected 7 entries from Day -7 through Day -1, will have their baseline value calculated as defined in Definition 1 above.
- Subjects with no entries from Day -7 through Day -1 but for whom ≥ 1 entry between Day 1 and Day 7 is available, will have their baseline value calculated as:

$$\frac{\text{sum of available entries from Day 1 through Day 7}}{\text{number of available entries from Day 1 through Day 7}}$$

- For subjects with no entries from Day -7 through Day 7, the baseline value will be missing.

Definition 3:

- Subjects with ≥ 1 of the expected 7 entries from Day -7 through Day -1, will have their baseline value calculated as defined in Definition 1 above.
- For subjects with no entries from Day -7 through Day -1, the baseline value will be missing.

Definition 4:

- Subjects with ≥ 4 of the expected 7 entries from Day -7 through Day -1, will have their baseline value calculated as defined in Definition 1 above.
- For subjects with < 4 entries from Day -7 through Day -1, the baseline value will be missing.

ASD = Asthma Symptom Diary; FAS = Full Analysis Set; SABA = short-acting beta agonist

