6.2.6.1 Symptom Scores

The ASD is a 6item daily measure of asthma symptom severity that assesses 3 core categories of asthma symptoms: breathing symptoms (difficulty breathing; wheezing; shortness of breath), chest symptoms (chest tightness; chest pain), and cough. The ASD is intended for twice daily completion and comprises a morning diary (for completion upon waking and referring to asthma symptoms during the nighttime) and an evening diary (for completion before going to bed and referring to asthma symptoms during the day).

Subjects are required to rate the 6 symptoms at their worst during the respective timeframes using an 11-point numeric rating scale ranging from 0 ('None') to 10 ('As bad as you can imagine') [6].

Individual morning and evening ASD symptom scores for the 6 symptoms of difficulty breathing, wheezing, shortness of breath, chest tightness, chest pain, cough will be reported for each symptom as recorded in the diary. If the assessment of a particular symptom is missing for either the morning or evening diary, then that symptom's score for that diary timepoint will be missing.

Mean symptom scores will be calculated for each symptom as the mean of the available scores for the applicable symptom for each week, as follows:

$$\frac{\text{sum of available entries for the week, for each symptom}}{\text{number of available entries for the week, for each symptom}}$$

A mean ASD score will be calculated as the mean of all available symptom scores for each week, as follows:

$$\frac{\text{sum of available entries for the week, for all symptoms}}{\text{number of available entries for the week, for all symptoms}}$$

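### The Day 1 fallback for the Asthma Symptom Diary baseline still needs a morning and an evening entry, so an early enrollee without a Day 1 morning entry has no ASD change from baseline

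*SAP*

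**What the plan says.** SAP 9.2 explains that Visit 1a, with diary activation, came in with Protocol Version 4.0, and that "subjects enrolled prior to this amendment did not have a diary activated until the day of randomization". The remedy follows: "To include such subjects in analyses, additional definitions of baseline have been included", under which "Day 1 entries or Day 1 through Day 7 entries may be used for calculation of baseline". The reason given is that background therapy is stable through the run-in and until Day 14, so these days represent baseline reasonably well.

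The table in SAP 9.2 then sets the rule for each measure:

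- **Mean symptom score and mean ASD score.** First choice: "at least 1 morning diary entry and at least 1 evening diary entry from Day -7 through Day -1" (for the mean ASD score, for each of the six symptoms). If that fails, the same morning-plus-evening condition applies to a window ending on Day 1. If that also fails, the baseline is missing.
- **SABA use, Definition 1.** If the diary was not active by Day -1, it is enough that "the diary was activated on Day 1 and ≥ 1 Day 1 entry is available".
- **Peak flow, Definition 1.** With no entries before Day 1, the Day 1 entry alone is the baseline.
- **SABA use and peak flow, Definition 2.** A Day 1 to Day 7 window is available.

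SAP 6.2.6.1 describes the diary as comprising "a morning diary (for completion upon waking and referring to asthma symptoms during the nighttime", together with an evening page completed before bed. Under SAP 9.1, change-from-baseline summaries "will include only subjects who have both a baseline value and corresponding value at the time point of interest".

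**The concern.** The fallback exists for subjects with nothing recorded before Day 1, so for them both required entries must come from Day 1 itself. One of the two belongs to the hours before a clinic visit, and the diary was activated only that day. A subject who has the Day 1 evening page but not the morning page falls through to a missing baseline. That is hard to square with the stated aim of keeping such subjects in. The ASD has neither the single-entry route nor the Day 1 to Day 7 route given to the other two diary measures, and the SAP does not explain the difference.

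Change from baseline in ASD score is a named secondary endpoint at Weeks 2, 4, 6, 8, 12 and 14. A subject with a complete follow-up diary could be lost from all six time points, and from all six individual symptom scores, because of a start-up circumstance.

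**Working it through.** The plan gives no figure on this point, so there is none to reproduce. The check is to apply the rules, then bound the size.

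**Step 1: apply the rules.** Take a subject with no entries from Day -7 to Day -1 whose diary is activated on Day 1.

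| Day 1 morning | Day 1 evening | ASD baseline | SABA baseline (Definition 1) |
|---|---|---|---|
| yes | yes | exists | exists |
| no | yes | missing | exists |
| yes | no | missing | exists |
| no | no | missing | missing |

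The second row is the pattern at issue.

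**Step 2: what is lost.** With a missing ASD baseline, Week 1 runs from Day 1 to Day 7 with one of seven morning entries absent. SAP 6.2.6.1 sets a weekly score to missing only when more than three morning or more than three evening entries are absent. The observed Week 1 score therefore survives, as do later weeks, and only change from baseline is lost. The subject stays in the Full Analysis Set, which needs a baseline and a post-baseline value of any efficacy assessment (SAP 7.1.3).

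**Step 3: number affected.** Let E be the number of early enrollees and q the share without a Day 1 morning entry. Neither is in the documents, so both are assumed. Suppose every evening entry is made. Missing ASD baselines = E × q.

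| E (of about 80) | q = 0 | q = 0.5 | q = 0.9 | q = 1 |
|---|---|---|---|---|
| 5 | 0 | 2.5 | 4.5 | 5 |
| 10 | 0 | 5 | 9 | 10 |
| 20 | 0 | 10 | 18 | 20 |

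The largest entry is 20/80 = 25%; the smallest is zero.

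**Step 4: upper bound on lost precision.** If a share s of each arm of 40 is lost, the standard error of a mean grows by 1/√(1 − s). Taking every early enrollee as lost (q = 1):

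- s = 0.05 (2 per arm): 1/√0.95 = 1.026, up 2.6%
- s = 0.10 (4 per arm): 1/√0.90 = 1.054, up 5.4%
- s = 0.25 (10 per arm): 1/√0.75 = 1.155, up 15.5%

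**Step 5: does the proposed baseline pair fit the weekly rule?** If the Day 1 evening and Day 2 morning entries form the baseline and Week 1 starts with the Day 2 evening page, Week 1 keeps mornings on Days 3 to 7 (five) and evenings on Days 2 to 7 (six). Counted against seven of each, that is 7 − 5 = 2 mornings and 7 − 6 = 1 evening short, both within the limit of three.

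**The case against.** The strongest reply is that the Day 1 morning page may well have been completed. No section gives the activation time, the visit time or a lock-out of that page, and completion on waking describes intended use, not what the device allowed. SAP 6.2.1 says that before a separate Peak Flow page existed, peak flow was collected on the ASD Morning page. The current protocol (Table 1, footnote 9) times daily peak flow between 10:00 AM and 2:00 PM and has it done at the clinic if it was missed at home; the timing in earlier versions is not given. A page carrying that measurement was probably usable well after waking. SAP 6.2.6.1 also starts Week 1 with the Day 1 morning diary, although that is a general rule for all subjects. This objection stands: it cannot be said that early enrollees usually lack the entry.

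A second reply is that the morning-plus-evening condition is deliberate. Weekly ASD means pool night and day scores, so a baseline with both kinds is comparable with them. SABA can accept one entry because its missing entries count as zero, which the ASD scores do not allow. This justifies keeping a morning-evening pair. It does not explain why the pair must be complete by Day 1, when SAP 9.2 itself accepts Day 1 to Day 7 entries as a fair picture of baseline.

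Third, the fallback is not empty. It serves early enrollees with both Day 1 entries, and subjects with partial entries before Day 1. That also stands.

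Finally, the ASD summaries are descriptive (n, mean, SD, median, minimum, maximum), so no planned test or interval changes.

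**Conclusion.** There is a real gap in the rule, of limited consequence. An early enrollee without a Day 1 morning entry has no ASD baseline and is lost from all ASD change-from-baseline summaries, despite the stated purpose of the fallback. How many such subjects exist is unknown and may be none. The standard-error increases of 2.6% to 15.5% are upper bounds on assumed shares. What is at stake is sample size in a descriptive secondary endpoint. Low priority.

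A reader might infer three stronger things that the documents do not support:

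- **That early enrollees as a group drop out of the ASD results.** Those with both Day 1 entries keep a baseline, and the documents do not say how many lack one.
- **That the same subjects necessarily stay in the peak-flow change results.** While peak flow sat on the Morning page, a missing page would remove the Day 1 peak-flow entry too. The contrast holds only once the separate page existed, and that change is not dated.
- **That the ASD rule affects the primary endpoint or biases the comparison.** ASD symptom scores do not enter the primary endpoint, and nothing in the documents ties a missing Day 1 morning page to treatment or outcome.

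**What to change.** In SAP 9.2, under mean symptom score and mean ASD score, add one further step. For a subject with no entries before Day 1 and no Day 1 morning entry, take the Day 1 evening and Day 2 morning entries as the baseline pair, and start that subject's Week 1 with the Day 2 evening diary. Flag these baselines in the listings, and report by arm the number of missing and the number of fallback ASD baselines. The counts will also show whether the gap ever mattered.

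The cost is a sentence or two in the SAP and a small change to the derivation. The downside is that the baseline rests on a single pair of entries and includes the first night after dosing. Two points make that tolerable: the step acts only where the baseline would otherwise be missing, and the existing fallback already admits a Day 1 evening entry on the SAP's stable-therapy argument. Copying the SABA single-entry rule would set an evening-only baseline against weekly means of both kinds. Copying the Day 1 to Day 7 window would put most of the baseline after the first dose and overlap Week 1. No extra evening-only table is needed.
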